H1: Older adults randomized to volunteering (vs. control) will report lower loneliness (H1a; UCLA Loneliness Scale)²⁷ and greater quality of life (H1b; WHOQOL Scale)²⁸ at 3, 6, 9, and 12 months.

Aim 2: *To examine increased social engagement, perceived usefulness, and perceived social support as mechanisms for reducing loneliness.*

H2: Older adults randomized to volunteering (vs. control) will report greater social engagement (H2a), perceived usefulness (H2b), and perceived social support (H2c) at 6 months, which will account for the effects on reduced loneliness at 12 months.

Aim 3: *To examine conditions under which volunteering is most effective at reducing loneliness.*

H3: The effect of volunteering vs. control on loneliness will increase with greater quantity (H3a; hours per month) and satisfaction (H3b).

H4 (exploratory): Given that functional impairment impacts all proposed mechanisms, the effect of volunteering vs. control on loneliness will be strongest for those with less functional impairment at baseline.

IMPACT: *National infrastructure for volunteering programs for older adults—The Senior Corps—ensures that volunteering is **highly scalable**. Dissemination and scaling up efforts will involve connecting primary care patients and aging services clients who are lonely with The Senior Corps, which we have shown to be feasible in our companion study, The Senior Connection. Existing infrastructure will make it possible to engage a large proportion of lonely older adults in volunteering, thereby reducing loneliness, improving well-being, and promoting health.*

II. CHARACTERISTICS OF THE RESEARCH POPULATION

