- **Follow-up assessments:** Subjects will be maintained in the study for 12 months. The initial intervention session (i.e., training) will begin within two weeks of randomization. Follow-up research assessments will be conducted for both conditions by email or mail at 3 and 9 months (or in-person if the subject does not have e-mail access and would prefer to complete them in-person) and in-person at 6 and 12 months. An assessment must be completed no later than two weeks after the target assessment date.

e) Assessment Measures & Administration Schedule:

The following tables specify the assessment measures we propose to use in the study:

Screening measures

Measure Name and Citation	Construct Measured	Description & Psychometric Data	Estimated Administration Time
Demographic characteristics	Not applicable	Age, gender.	1 minute
3-item UCLA Loneliness Short Form	Loneliness	A score of 6 or above has been shown to predict mortality. ^{18,29}	1 minute
6-Item Screener	Cognitive functioning	These 6 items ask questions measuring orientation and short-term memory.	1-2 minutes
National Institute on Alcohol Abuse and Alcoholism (NIAAA) single-item test	Alcohol misuse	This single item has greater than 90% sensitivity and specificity in the detection of alcohol use disorder.	1 minute Screening and 6 month visit
The CAGE Questionnaire ³⁰	Alcohol misuse	This 4 item questionnaire will be used as an exclusion screen. A	1 minute

		score of 2 or above is considered clinically significant.	Screening and 6 month visit
Self-Assessed Literacy Questions	Literacy	2 self-assessed questions regarding reading and writing abilities needed for the study	1 minute

Descriptive measures, and psychiatric/medical covariates

Measure Name and Citation	Construct Measured	Description & Psychometric Data	Estimated Administration Time
Demographic characteristics	Not applicable	Age, race/ethnicity, gender, sexual orientation, employment status (and history), income, education, living situation, marital status, PCP name, emergency contact, self-report endorsement of felony conviction.	3 – 5 minutes in-person interviews
Brief Grief Questionnaire ³¹	Grief	This brief self-report measure assesses social functioning impairment associated with bereavement.	1 minute in-person interviews if applicable

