Montreal Cognitive Assessment (MOCA) ³⁸	Global cognitive functioning	The Montreal Cognitive Assessment (MoCA) was designed as a rapid screening instrument for mild cognitive dysfunction. It assesses different cognitive domains: attention and concentration, executive functions, memory, language, visuoconstructional skills, conceptual thinking, calculations, and orientation. Time to administer the MoCA is approximately 10 minutes. The total possible score is 30 points; a score of 26 or above is considered normal. Nasreddine and colleagues report high sensitivity and specificity for MOCA scores in detecting MCI. ³⁸ The MOCA has three alternate forms in English to prevent practice effects with repeat administration, as well as a form for blind individuals.	10 – 15 minutes at baseline and final interview (alternate form used at final interview)
Columbia Suicide Severity Rating Scale (CSSRS) ³⁹	History of suicidal ideation and behaviors	The CSSRS is an interview that assesses for worst-point lifetime and past month suicidal ideation and behavior. It has been shown to predict future suicidal behavior ³⁹ and is the current gold standard for assessing suicide risk in clinical trials.	5 –15 minutes In-person interviews (time frame is “since last visit” for follow-up interviews)
Mood Improvement Protocol (MIP)	Self-perceived distress (before and after interview) and coping strategy (i.e., mood improvement activity)	The research interview may elicit negative reactions in individuals who are having difficulties in areas of their life related to questions in the assessment. Thus, this measure, adapted from procedures designed by Linehan and colleagues, is designed to enhance retention and improve subjects' experience in the research assessments.	5 – 10 minutes In-person interviews
Qualitative Feedback	Subject's experience in the research program	Open-ended questions to assess the subject's experience throughout the research program	5-10 minutes 6 and 12 month interviews
Volunteer Satisfaction Survey and Volunteer Benefits Survey	Subject's experiences in the volunteer program	Feedback to assess the subject's satisfaction and benefits from volunteering	5 minutes Volunteer condition only 6 month and final interview
Life Review Satisfaction Survey	Subject's experiences in the life review program	Feedback to assess the subject's satisfaction with life review	2 minutes Life Review condition only 6 month and final interview

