Behavioral Activation Scale for Depression (BADS)—social subscale ⁴⁵	Social activation.	Kanter and colleagues present evidence of the scale's psychometric properties, including solid factor structure, internal consistency, and test-retest reliability.	2-4 minutes in-person interviews
Volunteer Functions Inventory ⁴⁶	Reasons individuals participate in volunteer activities	Konrath and colleagues demonstrated good psychometrics	3-5 minutes Volunteer condition only

		and a latent structure consistent with several subscales.	6 months and final interview
PROMIS Social Functioning Computerized Adaptive Tests ⁴⁷	Emotional support, informational support, instrumental support, satisfaction with social roles and activities, social isolation, companionship	These computerized adaptive tests measure several domains of social functioning.	5 – 7 minutes In-person interviews
Rosenberg Mattering to Others Scale ⁴⁸	Mattering to others (5 items)	This is the most commonly used measure of perceptions of mattering and has numerous reports of solid psychometrics	2 – 3 minutes In-person interviews

Quality of Life measures

Measure Name and Citation	Construct Measured	Description & Psychometric Data	Estimated Administration Time
WHOQOL-BREF ²⁸	Health-related quality of life	This brief 36 item measure assesses several domains of health related functioning and quality of life. It has excellent psychometric properties and can be used cross culturally.	10 - 15 minutes baseline and final interview
PROMIS Quality of Life scales ⁴⁹	General life satisfaction, Meaning and Purpose, Positive Affect	These measure several domains of quality of life. The purpose in life items have been empirically linked to volunteering in older adults. ⁵⁰	4 - 6 mins in-person interviews
Reminiscence Functions Scale ⁵¹	Measures reasons individuals engage in reminiscence, which is a key component of the life review intervention.	Robitaille et al. provide support for the 8 subscales and data that demonstrate adequate psychometric properties in a sample of older adults.	6 – 8 minutes Life review only 6 month and final interviews
Brief Measure of Generativity and Ego Integrity ⁵²	Generativity (perceptions of giving back, especially to younger generations) and ego integrity (looking back on one's life with meaning)	Vuksanovic and colleagues ⁵² provide data indicating that this shortened measure provides adequate construct coverage.	2 – 4 minutes In-person interviews

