
Aim 1 compares subjects randomized to either the volunteering or control on loneliness (continuous variable). **H1a:** There will be a condition effect on loneliness at all time points indicating differing levels of loneliness in the direction: control > volunteering. Longitudinal models will be employed with loneliness as the response, and condition, time and their interaction as the predictors, controlling for age, gender. If a significant difference exists (a significant time by condition interaction), appropriate linear contrasts will confirm the hypothesized directional effects. For **H1b**, the same analytic strategy will be used, but with quality of life (continuous) as the response variable. Aim 2 involves mediation analysis: is to examine perceived usefulness and social support as mediators of the intervention effect on loneliness. **H2a:** Increases in social engagement at 6 months is hypothesized to mediate the effect of intervention condition on decreased loneliness at 12 months. The SEM-based mediation models will be applied, with social engagement as the mediator, intervention condition as the predictor and loneliness as the outcome, controlling for age, gender. If the null of full mediation is rejected, we will estimate direct, indirect and total effects to assess the strength of mediation. The same analytic strategy

will be used for perceived usefulness and social support (**H2bc**). **Aim 3** involves when volunteering will provide maximal benefit. **H3:** Greater hours (compliance) and satisfaction will be associated with better outcomes. We will apply the SFRM-based SMM to analyze dose-response relationships. We will first model dose using non-parametric methods and then characterize the patterns using parametric methods. This allows us to capture detailed dose and response relationships and provide more interpretable findings. **H4:** The longitudinal model for H1a will be used with functional status as a moderator variable.

h) Data and Safety Monitoring Plan:

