A Capacity for Informed Consent protocol will be implemented for all potential participants (see attached document: "Determination of Capacity for Informed Consent"). The capacity assessment will consist of a series of open ended questions administered to the subject that follow explanation of the study. It will address the subject's knowledge and understanding of the study's objectives, the voluntary nature of participation, ability to withdraw at any time, consequences of withdrawing, possible risks and benefits of participation. For subjects who have difficulty in one or more of these areas, further review of the relevant elements of the study will be provided in order to improve their knowledge and understanding to a level that enables them to make a meaningful choice about participation. A form (i.e., "Determination of Capacity for Informed Consent") will be completed for each subject documenting the results of the decision-making capacity determination, a copy of which is maintained with the consent form.

4. Debriefing Procedures

At the final 12 month interview, research staff will give those assigned to life review information about volunteering. If they are interested, a Lifespan brochure that lists all Lifespan programs and contact information will be given to the subject.

5. Consent Forms

See attached.

6. Documentation of Consent

All signed consent forms will be stored in a locked file in a locked office, separate from other non-identifying subject data. Only study staff will have access to these files. All subjects will receive a signed copy of the consent form for their records.

7. Costs to the Subject

There are no costs to the subject. Parking at URMC will be paid for by the study. For those who take the bus, a bus pass will be provided.

8. Payment for Participation

Participants will be paid \$50 for the baseline interview, \$10 for each internet-based/mailed/in-person survey follow-ups (3 and 9 months), and \$35 for in-person interviews at 6 and 12-months. Each participant, therefore, may be reimbursed a maximum of \$140 for their time and effort.

References

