Due to Covid-19 restrictions, all study visits are remote. These changes will remain in effect until URMC/NIH guidance changes regarding research and our high risk population (people over the age of 60). We have reassessed safety procedures and obtained DSMP guidance and will allow volunteer activities that RSVP has approved for volunteering. These agencies will have a documented safety plan and will be reviewed by members of our DSMP Committee. Any subject wishing to participate in at home volunteer activities may still continue to do so. Any additional changes will be reviewed by our DSMP committee and discussed with program officer before we will revert to our original protocol and resume all in-person activities.

Study visits – Baseline, 6 months and 12 months will be conducted via phone or zoom and online. 3 and 9 month surveys will remain remote either online or by phone. If a subject is unable or unwilling to use zoom, the visits will be done by phone with self-administered studies sent by e-mail.

Consent – Consent will be done at the baseline visit over the phone or through zoom. At the screening call, the study coordinator will ask the subject whether they want to use phone or zoom. E-consent will be done through the REDCap module. The study team will obtain verbal permission to send the eConsent via email. Verbal permission will state: “Because URMC can’t control the security of email messages once we send them, we need your permission to email you. Do you want to receive the link to the eConsent via email?” The permission will be documented. The email will not include PHI.

To verify the subject’s identity - the study team will add security questions to answer at the time of accessing the survey/eConsent. These questions will be pre-established security questions such as “What is your favorite color?” or “What is the name of the street you grew up on?” that are included on the signature page of the eConsent. The responses will be agreed upon by both the study team and the subject during the screening call. The answers will be saved in the subject record for verification later.

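### H1b predicts a WHOQOL effect at four follow-up times, but the WHOQOL-BREF is scheduled after baseline only at month 12

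*Combined protocol and SAP*

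**What the plan says.** - **Hypothesis (section I, Specific Aims & Hypotheses).** H1 predicts lower loneliness (H1a, UCLA scale) "and greater quality of life (H1b; WHOQOL Scale"), both "at 3, 6, 9, and 12 months".
- **Schedule (section III.e, Quality of Life measures).** The timing entry for the WHOQOL-BREF is "10 - 15 minutes baseline and final interview". The UCLA Loneliness Scale, by contrast, is given at all time points.
- **Analysis (section III.g, Aim 1).** H1a uses a longitudinal model with condition, time and their interaction, adjusted for age and gender, with contrasts to follow a significant interaction. For H1b, "the same analytic strategy will be used, but with quality of life (continuous) as the response variable".
- **Visits (section III.d, Follow-up assessments).** Follow-up is by email or mail at months 3 and 9 "and in-person at 6 and 12 months".
- **Addendum of 2/9/22.** The visit times are kept: "3 and 9 month surveys will remain remote either online or by phone". Among existing measures only the MOCA is adjusted. Two new measures are added, and neither is a quality of life scale.

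**The concern.** The hypothesis and the schedule cannot both be followed. H1b claims an effect at four follow-up times on a named instrument, and that instrument is collected at one of them. An analyst working from the plan would have no WHOQOL response at months 3, 6 or 9, and a time-by-condition model with only two levels of time.

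Quality of life is part of the study purpose and of Aim 1. If the mismatch stays, a 12-month result could be reported as though it met a four-time-point hypothesis. Another quality of life scale could also be substituted at month 6 once data are in hand.

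**Working it through.** **1. Same instrument?** H1b and the WHOQOL-BREF row both cite reference 28, the WHOQOL-BREF development paper. They mean the same scale.

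**2. What is the final interview?** Section VII.4 (Debriefing Procedures) fixes it: "At the final 12 month interview". The Volunteer Satisfaction Survey row in section III.e has "Volunteer condition only 6 month and final interview", so month 6 and the final interview are separate visits. The WHOQOL-BREF is therefore given at months 0 and 12.

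**3. Gap.** Hypothesised times {3, 6, 9, 12} minus scheduled times {0, 12} leaves {3, 6, 9}. That is 3 of 4 follow-up times with no planned WHOQOL data.

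**4. Could another scale fill it?** The PROMIS Quality of Life scales are given at in-person interviews, which are baseline, 6 and 12 months. {3, 6, 9, 12} minus {0, 6, 12} still leaves {3, 9}. H1b does not name these scales in any case.

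**5. What the Aim 1 model becomes.** With WHOQOL at months 0 and 12 only, the time-by-condition interaction is a single contrast: the arm difference at month 12 minus the arm difference at baseline. An arm comparison at month 12 adjusted for baseline addresses the same question with smaller variance.

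**6. Illustration of that difference.** The plan gives no power statement and no correlation for quality of life, so the baseline-to-12-month correlation r is assumed. Other inputs:
- 150 baselines per arm and 20% attrition (section III.g), so 150 × 0.8 = 120 completers per arm.
- Two-sided 0.05 and 80% power, as in the plan's loneliness calculation; unit SD.
- Detectable effect = (1.960 + 0.8416) × √(2v), where v is the per-arm variance.
- Baseline-adjusted: v = (1 − r²)/120.
- Two-visit likelihood model testing the interaction: v = (1 − r²)/120 + (1 − r)²/150.

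| Assumed r | v, adjusted | Detectable, adjusted (SD) | v, interaction | Detectable, interaction (SD) | Variance ratio |
|---|---|---|---|---|---|
| 0.3 | 0.00758 | 0.345 | 0.01085 | 0.413 | 1.43 |
| 0.5 | 0.00625 | 0.313 | 0.00792 | 0.353 | 1.27 |
| 0.7 | 0.00425 | 0.258 | 0.00485 | 0.276 | 1.14 |

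Worked line for r = 0.5, adjusted: (1 − 0.25)/120 = 0.00625; 2.8016 × √0.0125 = 0.313.

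The within-subject correlation of 0.3 in section III.g was set for loneliness; nothing in the plan says it applies to the WHOQOL.

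**7. Burden of the alternative.** Three extra administrations × 10 to 15 minutes = 30 to 45 minutes per participant.

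**The case against.** The contradiction in the text is not open to dispute, but its reach is.

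- **Quality of life is not wholly unmeasured before month 12.** The PROMIS scales are planned at month 6, and the Aim 1 analysis text gives the H1b response only as a continuous quality of life variable. This stands as a limit: what is lost is WHOQOL data, not all quality of life data. It does not rescue H1b, which names the WHOQOL.
- **Months 3 and 9 may be in person for some.** Section III.d allows this for participants without e-mail who prefer it, and whether PROMIS would then be given is unclear. The exception covers a subset and supplies no WHOQOL data.
- **The detectable effects do not measure the defect.** They compare two analyses of the same two visits, under an assumed correlation. That is correct; the size of the defect is 3 of 4 time points.
- **The interaction test is valid with two visits.** It is, and its disadvantage shrinks as the correlation rises. Correcting the time points is necessary; changing the model is a gain in efficiency and clarity.
- **Other repairs exist.** The sponsor could keep the WHOQOL at month 12 and also name the PROMIS scales at months 6 and 12 without new data. That is a legitimate choice, but it adds a second instrument to H1b and still leaves months 3 and 9 empty.

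**Conclusion.** The concern holds. H1b is untestable at 3 of its 4 stated time points because its instrument is not scheduled there. This follows from the documents alone and needs no assumption; only the detectable effects rest on an assumed correlation. The 12-month WHOQOL comparison remains available.

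The consequence is limited. Section III.g ties the primary hypotheses and the sample size to loneliness, and the UCLA scale is collected at every visit, so H1a is unaffected. The point should be fixed, but it does not threaten the trial's main result.

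**What to change.** - **Section I.** Keep the four time points for H1a and restate H1b as greater WHOQOL-BREF quality of life at 12 months.
- **Section III.g, Aim 1.** For H1b, replace the carried-over time-by-condition step with a single between-arm comparison at 12 months, adjusted for baseline WHOQOL, age and gender. The same edit should name the WHOQOL-BREF score or domain used and say how missing 12-month values are handled.

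The cost is one hypothesis sentence and one model sentence, with no new visits or data. The price is a narrower claim, with nothing said about the WHOQOL at months 3, 6 or 9.

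Adding the WHOQOL-BREF at those months is the weaker option. Besides the extra burden, participants already past those visits could not contribute, so the early time points would be incomplete.

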Attitudes to Ageing Questionnaire AAQ	Feelings on getting older	This set of self-report questions allow subjects to express their attitudes towards aging.	5 minutes In-person interviews

Total estimated time for entire baseline interview		90 – 153 minutes
--	--	------------------

f) Study Conditions:

Volunteering condition: HOPE volunteers are supported by Lifespan and the Senior Corps. The Senior Corps is one of Lifespan's many programs for seniors in the community. Its objective is to match seniors with volunteer opportunities that match their interests and capabilities. Subjects will begin training at Lifespan within two weeks of randomization. Aging Services agency-supported volunteer placement in a social volunteer activity is initiated for one year. The target expectation for volunteering is 4 times per month (about once per week). Lifespan collects monthly timesheets, which will include the number of hours and types of volunteer

activities done. The Senior Corps provides a small reimbursement for travel to volunteers as needed for travel related to volunteering. The other component of the intervention is on-going training (“booster sessions”), volunteer support groups, and educational activities offered by Lifespan. These gatherings for volunteers serve to promote retention in the program, assist volunteers with any problems/issues that have arisen, and promote social connectedness among volunteers. This is standard Lifespan policy.

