Control Condition: The active control group was chosen to control for (and minimize confounding by) potential non-specific effects of participating in a study intervention; expectancies about benefit; and starting a new cognitively engaging activity. Subjects randomly assigned to the active control group will complete a self-guided life review exercise over 12 months.^{53,54} This standardized and evidence based intervention is commonly used to reduce depression and promote well-being in later life; further, it was recently tested (and validated) as a self-guided intervention to improve well-being by Lamers and colleagues⁵⁴; life review was also used as a control condition for a NIA-funded randomized trial of problem solving therapy for older patients with macular degeneration (R01AG032032, [name], PI)⁵³ that was recently completed in the UR Department of Psychiatry. [name] will be available to advise the HOPE team regarding implementation of this condition. To minimize the social nature of providing the intervention (i.e., minimizing confounding our conditions), the life review will be largely self-guided, including replacing the counselor (and one-on-one sessions) with email support and a self-help book, per the protocol of Lamers and colleagues.⁵⁴ Subjects will complete two sections of the life review (with the self-help book) each month and send ‘assignments’ twice per month to an email ‘counselor’ who will respond with supportive comments within three days (per Lamers et al., protocol). The minority of subjects who do not have access to email will be provided the opportunity to participate via regular mail. The Lamers and colleagues’ intervention was found to enhance psychological well-being. Studies examining individual life-review, including [name]’s, indicate that life review reliably reduces depressive symptoms, but does *not* reduce loneliness (though group life review may increase social integration).⁵⁵ Further, life review is associated with high compliance rates, comparable to—or exceeding—compliance rates for other evidence based interventions for older adults.^{53,56} These data indicate that life review will represent a *face valid* intervention for subjects, thus increasing expectancies of positive benefit and promoting compliance and retention. Our active control condition will provide benefit to subjects without reducing loneliness, thus addressing one of the largest confounds for behavioral interventions, especially interventions of an extended duration—expectancy effects^{57,58}—while also promoting high compliance rates.

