The ITT analysis for Aim 1 provides intervention effects averaged over all subjects randomized to the intervention conditions. When intervention compliance (volunteering hours/satisfaction for subjects in the volunteering condition) demonstrates a dose-response relationship, as we hypothesize in Aim 3, complier average causal effects (CACE) are appropriate; thus we will use them to test Hypothesis 3. CACE is a compliment to ITT analyses and provides an answer to a different question than is answered by ITT analyses (i.e., the result of complying vs. being offered an intervention).⁷¹ CACE provides valid causal inference because it maintains randomization and includes all subjects in the analysis, as with ITT.⁷² CACE provides different intervention effects for individuals depending on their levels of compliance, which can be quite informative, especially when there is large variability in intervention compliance and strong dose-response relationships. The ITT and CACE estimates from a similar intervention study by Gruenewald, et al.⁷³ show that not only were the CACE effect sizes much larger than their ITT counterparts (small ITT vs. large CACE effect size), but the temporal trend also reversed; while the ITT effect sizes decreased, the CACE effect sizes increased from 4 months to 12 months post intervention, indicating substantial heterogeneity in intervention compliance and strong dose-response relationships. Since volunteering time is only required for the volunteering condition, standard statistical models cannot be used to perform CACE analysis. The CACE approach enables an estimate of the treatment effect at each level of "compliance" (i.e., amount of hours volunteered), without the need for a measure of compliance in the control group. In this way, we will be able to tell how well volunteering reduces loneliness at different "doses" of volunteering. The two most popular methods for addressing intervention compliance are the parametric principal stratification (PS) and the semi-parametric structural mean model (SMM).⁷⁴⁻⁷⁶ Unlike the PS, the SMM not only allows for continuous dose variables, but also requires no parametric model for data distribution such as normality, thereby yielding robust inference for a broader class of data distributions. We will use the latest SMM based on the structural functional response models (SFRM) for our CACE analysis, which not only allow for continuous, but also multiple dose variables.⁷⁴⁻⁷⁶ We are particularly interested in potential non-linear dose-response relationships so that we may determine optimal dose intervention whereby increased exposure (i.e., number of hours volunteered) becomes less worthwhile (in terms of reducing loneliness).

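### The H3 hours slope needs the assumption that assignment affects loneliness only through hours volunteered, and the plan neither states nor tests it

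*Combined protocol and SAP*

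**What the plan says.** Section I (Specific Aims & Hypotheses) makes hours per month the dose for H3a and satisfaction the dose for H3b, with loneliness as the outcome. Section III.g (Analytic Procedures) defines compliance as "volunteering hours/satisfaction for subjects in the volunteering condition", so dose exists in one arm only. The estimator is named: "We will use the latest SMM based on the structural functional response models (SFRM) for our CACE analysis". The approach is said to work "without the need for a measure of compliance in the control group". The argument for its validity is one sentence: "CACE provides valid causal inference because it maintains randomization and includes all subjects in the analysis". The dose curve is to be modelled non-parametrically and then parametrically, and one aim is to find the number of hours beyond which more volunteering adds little.

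Section III.f describes the two arms. Volunteers start training at Lifespan within two weeks of randomization, and Lifespan's monthly timesheets record the hours and types of volunteer activity. A further component of the intervention is booster training, "volunteer support groups, and educational activities offered by Lifespan". These gatherings are meant to help retention, to deal with problems, "and promote social connectedness among volunteers". Controls receive 12 months of self-guided life review. On its effect the protocol is explicit: "Our active control condition will provide benefit to subjects without reducing loneliness".

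The plan does not say whether the dose curve is held at zero at zero hours, or whether training and gatherings count as dose.

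**The concern.** Randomization makes the arms comparable, so the ITT difference can be read causally. It does not by itself say which part of the assigned programme produced the difference. To turn the ITT difference into an effect per hour, the model also needs an exclusion restriction: a person assigned to volunteering who logs no hours would have the same loneliness as under assignment to life review.

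Section III.f gives a concrete reason to question that. Part of the volunteering arm's programme is designed to act on social connectedness and is not hours volunteered. The comparator is also an active programme, so zero hours in the volunteering arm is not the same condition as control.

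At stake is what H3a means. Benefit from training and gatherings would be credited to hours. Any benefit of life review on loneliness would be subtracted from them. The optimal-hours statement, which is meant to inform a programme that the protocol calls scalable, would carry the same error.

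**Working it through.** The documents give no slope, dose distribution or power for H3, so there is no stated figure to reproduce. The check is algebra, then an illustration with assumed inputs.

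**Model.** Let the true effect of assignment for someone with D hours be ψ0 + ψ1·D. Here ψ0 is the net effect on loneliness of everything other than hours: Lifespan training and gatherings, minus life review. Negative values mean less loneliness.

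- ITT difference = ψ0 + ψ1·E[D].
- A linear hours-only model with the effect at zero hours set to zero estimates ITT / E[D] = ψ1 + ψ0 / E[D].
- The shift is therefore ψ0 / E[D]. As a fraction of the true slope it is ψ0 / (ψ1·E[D]).

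The shift is zero only if ψ0 = 0. If the non-hours effect varies between people, its arm average takes the place of ψ0.

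**Assumed inputs (not in the documents).** Outcome SD 1; 20% of the volunteering arm at zero hours; the rest averaging 6 hours per month, so E[D] = 0.8 × 6 = 4.8; and an hours effect of 0.2 SD at the mean dose, so ψ1 = −0.2 / 4.8 = −0.0417 SD per hour. The 0.2 is borrowed from the effect size in the plan's ITT power statement, as a reference size only.

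| ψ0 (SD) | ψ0 / 4.8 | Estimated slope | Relative to true slope |
|---|---|---|---|
| −0.10 | −0.0208 | −0.0625 | overstated by 50% |
| −0.05 | −0.0104 | −0.0521 | overstated by 25% |
| 0 | 0 | −0.0417 | correct |
| +0.05 | +0.0104 | −0.0312 | understated by 25% |
| +0.10 | +0.0208 | −0.0208 | understated by 50% |

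The relative shift depends only on the ratio of offset to hours effect. With an hours effect of 0.5 SD at the mean dose, a 0.05 SD offset shifts the slope by 0.05 / 0.5 = 10%.

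**Simulation** (2,000 trials per setting, 150 per arm, same assumptions). Mean slopes agreed with the formula to about 0.001. With no true hours effect, a nominally significant slope appeared in 5.6% of trials at ψ0 = 0, 7.8% at −0.05 and 13.5% at −0.10.

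**Estimating the zero-hour effect instead of fixing it.** Using arm and arm-by-covariate as instruments, with one baseline covariate that predicts hours, the median slope stayed between −0.039 and −0.047 in every setting with a true slope of −0.0417. Its spread rose from about 0.024 to about 0.078, a factor of 0.078 / 0.024 ≈ 3.

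**The case against.** Four points on the other side have force.

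- *Attendance.* A reader might infer that volunteers with no hours still attend the support groups. The documents do not show this. The sessions are offered, they are described as gatherings for volunteers, and only initial training is scheduled for everyone. If attendance rises in proportion to hours, there is no zero-hour offset from gatherings, and the slope is the effect per hour of the whole programme, which is a matter of labelling. This stands, but only in part. The ITT difference contains the average effect of gatherings whoever attends them, so a slope described as the effect of volunteering hours still absorbs it. Initial training also comes early, whereas a placement waits on a background check and matching (section III.d).
- *Life review.* A reader might infer that the active control by itself biases the slope. The Control Condition text states that individual life review does not reduce loneliness, and loneliness is the H3 outcome. On that premise this route contributes nothing. It matters only if the premise fails, for example through expectancy acting on a self-reported outcome.
- *Model form.* The exclusion restriction is usual for such models, but the plan does not say that the curve is fixed at zero. It allows several dose variables, and its exact form lies in cited sources. So the documents do not support saying flatly that the slope is biased.
- *Size.* An offset of 0.10 SD is half the effect size of 0.2 in the power statement, and the two routes have opposite signs, so the net could be close to zero. This stands: the figures above are illustrations.

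**Conclusion.** The point holds as a conditional one. The validity argument in section III.g is incomplete. If the model sets the effect at zero hours to zero, the H3a slope is shifted by the net non-hours effect divided by mean hours, and it is unbiased only if that net effect is zero. Section III.f supplies a plausible reason why it may not be. Its size and sign cannot be learned from the documents. The 25% shift for a 0.05 SD offset rests on an assumed offset and an assumed 0.2 SD hours effect at the mean dose.

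The documents do not establish that bias is present, that zero-hour volunteers attend gatherings, or that life review changes loneliness. Nor does the point reach the trial's main result: H3 belongs to Aim 3, and the Aim 1 ITT comparison of the two assigned programmes needs no such assumption.

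**What to change.** 1. In section III.g, replace the sentence that derives validity from randomization and full inclusion. State that the H3 estimate is relative to life review and assumes that assignment has no effect on loneliness at zero hours.
2. Report the H3a slope, and any optimal-dose statement, over a pre-stated grid of zero-hour effects, for example −0.10, −0.05, 0, +0.05 and +0.10 SD. In the linear model each grid value gives slope = (ITT − ψ0) / E[D]. For an illustrative ITT difference of −0.2 SD and mean hours of 4.8, the slopes run from (−0.2 + 0.10) / 4.8 = −0.021 to (−0.2 − 0.10) / 4.8 = −0.0625. The non-parametric curve can be anchored at the same values.
3. If Lifespan already holds attendance records for training and gatherings, enter attendance as a separate second dose, which the chosen model allows. Do not add it to volunteering hours: that would treat an hour in a support group as equal to an hour of volunteering and would change the dose named in H3a. One random assignment does not separate two slopes without further information, so name in advance the baseline covariates relied on.

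Steps 1 and 2 need no new data, only revised text and a few extra model runs. Step 3 depends on existing records. The protocol is dated 2019 and the addendum 2022, so logging started late would miss earlier participants. The price is that H3 is reported as a range and its conclusion is less sharp.
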